To compare the intervention (MBCT + TAU) with the waitlist-control (TAU only) group on sociodemographic, outcome, and hypothesized mediating and moderating variables, independent-samples t-test or chi-square test will be used. The effect of treatment (MBCT + TAU versus TAU) will be tested in the intention-to-treat sample using latent growth curve models (LGCM; (Duncan & Duncan, 1995)). The intercept (baseline score of dependent variable) and slope (representing change over time) will be modeled as latent variables from data at pre-treatment (T0), mid-treatment (T1) and post-treatment (T2) (see Figure 1). First, unconditional models will be estimated separately in each group (MBCT + TAU versus TAU) to test whether a linear (0, 4 and 8 weeks) or non-linear trend of change over time would fit the data best. Second, group (MBCT + TAU = 1 ; TAU = 2) will be added to the model as predictor of the latent growth factors. The path from Group to Slope reflects differences in the trajectories of change on the outcome measure(s) between groups whereas the path from Group to Intercept reflect baseline differences on outcome measures. To assess the rate of change within each group, within-subject cohens d effect sizes will be calculated by dividing the mean-difference (T2-T0) by the standard deviation (SD) of the difference, with 0.2, 0.5, 0.8 representing small, medium and large effects respectively. To compare the rate of change between groups, a between group effect size for growth modeling analysis (GMA) will be calculated using the following equation:
$$\frac{\beta_{11} \times \text{time}}{\text{Pooled SD raw scores}}$$

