To test for mediation of the effect of MBCT + TAU versus TAU on depressive symptoms (primary outcome; IDS-SR) and overall functioning (secondary outcome; OQ-45) by primary (the different RNT measures (RRS brooding subscale, PTQ, negative intrusive thoughts on BFT) and secondary mediators of interest (FFMQ, SCS)), cross-lagged structural equation models (CLSEM) will be run (Figure 2) in the per protocol sample. For the primary analysis we deliberately choose for a CLSEM approach instead of using the frequently used Process Macro by Hayes (Hayes et al., 2017) (on which power calculation was based) because of practical and content-related reasons. We choose for CLSEM because (i) the nature of the data. We anticipate to have relatively more missing data at specific time points (i.e. the first, second or third measurement moment) because of the COVID-19 pandemic. CLSEM can handle missing data whereas with PROESS all participants with at least one score missing at one of the time points will be deleted from analyses. (ii) CLSEM provides more information on how variables change (each other) over time, i.e. we model (iia) autoregressive and (iib) cross-lagged effects. And (iii) CLSEM enables modeling of individual participants, and because of that, within-person processes can be separated from stable between-person differences by means of inclusion of random intercepts.

Thus, separate three-wave CLSEM will be run to test mediation of the effect of group by potential mediators on outcome measures (IDS-SR and OQ-45). We will include the following paths within those models: autoregression effects (stability effects) for mediators and outcome variables,

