within time correlations between mediator and outcome variables, longitudinal cross-lagged effects of mediator and outcome variables, effect of outcome at T0 on outcome at T2 and mediator at T0 on mediator at T2. In addition, we will test whether group (MBCT + TAU versus TAU) will have a significant differential effect on outcome at T2 (path a), on mediator at T1 (path b), and whether mediating variables at mid-treatment (T1) predict outcome post-treatment (T2). Finally, as a formal test of mediation, the indirect effect of group (MBCT + TAU versus TAU) on outcome at post-treatment (T2) via mediating variables at mid-treatment (T1) will be estimated using bootstrapping procedures (Selig & Preacher, 2009) consisting of 5000 bootstrap samples. We will calculate 95% confidence intervals (CI) of indirect effects (Preacher and Hayes, 2008). To separate within-person processes from stable between-person differences we will repeat the CLSEM models with the inclusion of random intercepts (Hamaker et al., 2015; Mulder & Hamaker, 2021), and compare results.

[figure not shown]

Figure 2. Structure of Cross-Lagged Structural Equation Models (CLSEM) of mediation for outcome at post-treatment (T2) by mediator at mid-treatment (T1). a represents the direct path of group on outcome, b the effect of group on mediator at mid-treatment, c the effect mediator of mid-treatment on outcome at post-treatment, while $b \times c$ represents the indirect path from group on outcome at post-treatment via mediator at mid-treatment. Note. Group = Mindfulness-based Cognitive Therapy (MBCT) + Treatment as usual (TAU) versus TAU, T0 = pre-treatment, T1 = mid-treatment, T2 = post-treatment.

As a sensitivity analysis we will perform a simple mediation analysis by using the PROCESS macro provided by Hayes et al. (2013). Group (MBCT + TAU versus TAU) will be entered as IV, pre- to post-treatment residualized change in depressive symptoms (IDS-SR) as DV, while pre- to mid-treatment residualized change in RNT/rumination (PTQ/RRS brooding subscale) will be entered as mediator. Other potential mediators of interest will be tested in an analogues manner.

Secondary outcomes: experimental tasks

1. Pavlovian to Instrumental Transfer Task

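### As written, the primary mediation model has no group path to the outcome at T1, which biases path b and the formal test b×c if MBCT already moves symptoms by mid-treatment

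*SAP*

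**What the plan says.** The Mediation analyses section describes a three-wave cross-lagged model. Its path list contains "autoregression effects (stability effects) for mediators and outcome variables", then "within time correlations between mediator and outcome variables, longitudinal cross-lagged effects of mediator and outcome variables", then one T0→T2 path for the outcome and one for the mediator. Group enters in a separate sentence, which asks if "group (MBCT + TAU versus TAU) will have a significant differential effect on outcome at T2 (path a), on mediator at T1 (path b"). The same sentence tests the mediator at T1 as a predictor of the outcome at T2 (path c in the Figure 2 caption). The caption reads "a represents the direct path of group on outcome, b the effect of group on mediator at mid-treatment" and makes b×c the indirect path. The bootstrap interval for that product is the formal test of mediation.

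Two further analyses follow. For the first, "we will repeat the CLSEM models with the inclusion of random intercepts". For the second, "As a sensitivity analysis we will perform a simple mediation analysis by using the PROCESS macro".

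Elsewhere, under Clinical effects of MBCT, the growth model has group predict a slope factor over T0, T1 and T2: "The path from Group to Slope reflects differences in the trajectories of change on the outcome measure(s) between groups". The candidate shapes are a "linear (0, 4 and 8 weeks) or non-linear trend of change over time would fit the data best".

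**The concern.** With no group→outcome T1 path, the model fixes that effect at zero. The T1 residual correlation between mediator and outcome is free, so a real group difference in symptoms at T1 is absorbed elsewhere, and it lands in b. The fitted b is then the group difference in RNT adjusted for symptoms at T1, a variable that treatment may already have changed. That is not what the caption says b is.

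The growth model is hard to reconcile with a zero effect at T1. As described it has one slope factor, so a group effect at T2 implies half that effect at T1 under the linear form. Under a non-linear form it implies some share, unless the shape has no change at all by T1.

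What is at stake is the primary mechanistic conclusion. If MBCT lowers both RNT and symptoms by mid-treatment and their residuals correlate positively, mediation is understated. If symptoms fall by T1 and RNT does not, the model produces a spurious indirect effect of opposite sign.

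**Working it through.** **Why b shifts.** Let X be the T0 scores, M1 and Y1 the T1 mediator and outcome, g the true group effect on Y1, and κ = σMY/σYY from the T1 residuals.

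- Truth: M1 = b·G + X terms + eM and Y1 = g·G + X terms + eY, with eM = κ·eY + u.
- Substituting eY = Y1 − g·G − X terms gives M1 = (b − κg)·G + κ·Y1 + X terms + u.
- If the Y1 equation has no G, all information on G at T1 comes from this conditional equation. Complete-data ML therefore returns b* = b − κg.
- The bias is zero only if g = 0 or the residual correlation is 0. Path c is not affected by this particular omission.

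**Anchors from Sample size – power calculation.** Correlations are .18 (group with outcome), .27 (group with mediator) and .26 (mediator with outcome). A simulation of simple mediation from these three, with 95% Monte Carlo intervals, gives power of 78.5% at N = 174 and 81.9% at N = 180. The stated 174 is therefore reproduced closely if the unstated target is 80%. With equal groups, coded MBCT = 1 and TAU = 0 so that a reduction is negative:

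- b = −.27/.5 = −0.54 SD (taken as the T1 effect)
- group effect on outcome at T2 = −.18/.5 = −0.36 SD
- c = (.26 − .27×.18)/(1 − .27²) = .2114/.9271 = .228
- true b×c = −0.54 × .228 = −0.123

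**Assumptions.** The SAP gives neither g nor the T1 residual correlation ρ. I took ρ = .26, .4 and .6, and g = −0.09, −0.18 (linear trend: half of −0.36) and −0.36 (whole effect by T1). Residual variances are 1, so κ = ρ.

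**Result: b\* = −0.54 − ρg, with b×c as a percentage of truth.**

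| g | ρ = .26 | ρ = .4 | ρ = .6 |
|---|---|---|---|
| −0.09 | −0.517 (96%) | −0.504 (93%) | −0.486 (90%) |
| −0.18 | −0.493 (91%) | −0.468 (87%) | −0.432 (80%) |
| −0.36 | −0.446 (83%) | −0.396 (73%) | −0.324 (60%) |

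ML fits of the listed model to population covariances agree with the formula. Adding the group→outcome T1 path returns b = −0.54.

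**If true b = 0**, b* = −ρg. This runs from +0.047 (.26 × .18) to +0.216 (.6 × .36), the wrong sign.

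**Simulation.** N = 170 (200 × .85), 2000 replications, Monte Carlo interval for b×c. Assumed autoregressions are .5, T0→T2 paths .15, other cross-lags .1 and a = −.15. The simulation error of each percentage is about 1 point.

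- Power at g = −0.18, listed versus corrected model: 79 vs 82% (ρ = .26) and 71 vs 70% (ρ = .6), so little change.
- Power at g = −0.36: 70 vs 79% (ρ = .26) and 56 vs 70% (ρ = .6).
- Wrong-direction intervals when true b = 0: about 5–10% (g = −0.18) and 10–29% (g = −0.36), against 1–3% with the paths added.

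A separately coded simulation at N = 174, with other assumed coefficients, points the same way. With b = 0 and the whole effect present by T1, b×c is rejected in 13% of trials (ρ = .26) and 31% (ρ = .5), instead of 4–5%.

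**Would model fit reveal it?** The omission adds noncentrality N·ln(1 + .25g²) to a 4-df chi-square. That is 170·ln(1.0081) = 1.37 for g = −0.18 and 170·ln(1.0324) = 5.42 for g = −0.36. Power to see misfit at the 5% level is about 13% and 43%.

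**Group→mediator T2.** The same mechanism acts at T2. With an assumed true effect of −0.1 to −0.2, omitting this path inflates c by 1–7% and moves path a from −0.15 to between −0.12 and −0.03. With both paths omitted, b×c is 62–93% of truth for g between −0.18 and −0.36.

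**The case against.** The best reply is that the omission is read from the text while the drawing that defines the model is not visible. The explicit path list contains no group paths at all. Group appears in a sentence about what will be tested, and a caption need letter only the paths that form the direct and indirect effects. Nothing says the group→outcome T1 path is fixed at zero. This stands as a limit on the claim: the point concerns the written specification, and Figure 2 may already resolve it. Even so, the text is what an analyst would code from, and it names two group paths and no others.

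Second, the growth model allows a T1 effect but does not assert one. That is true, but b is free of bias only if there is no effect by T1 or no T1 residual correlation. The first would need a shape with no change in the first half of treatment.

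Third, the effect is modest where it is best anchored: 91% of truth and almost no loss of power at the linear trend with ρ = .26. When both effects run the same way, the bias is conservative for claiming mediation. This also stands. The large losses require most of the symptom effect to be present by T1, and power differences of about 3 points are close to simulation noise.

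Fourth, the PROCESS analysis estimates group→mediator change without outcome T1 and so lacks this bias in b. But it is a sensitivity analysis, and the SAP itself rejects PROCESS as primary because it drops anyone with a missing score.

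**Conclusion.** The concern holds for the model as written and should be fixed. The formal test b×c is biased whenever MBCT has changed symptoms by T1 and the T1 residuals correlate. The formula is exact for complete-data ML. The size is a range that rests on assumed values of g and ρ: b×c at 80–91% of truth under a linear trend, and 60–83% if the whole effect is present by T1. Under the linear trend, power is essentially unchanged and the harm is to the estimate and its interval. The more serious case is true b = 0, where wrong-direction intervals become several times more frequent than they should be. The group→mediator T2 omission is secondary for b×c but can change path a substantially. If Figure 2 already draws both paths, what remains is to bring the text into line with it.

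**What to change.** State in the path list that group→outcome T1 and group→mediator T2 are estimated, or confirm that Figure 2 contains them and say so in words. Keep b×c from that model as the mediated effect, and report the route group→outcome T1→outcome T2 separately.

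Cost in the main model: seven variables give 7×8/2 = 28 moments. The listed model has 6 (group and T0 moments) + 12 paths + 6 (T1 and T2 residual moments) = 24 parameters, df 4. The corrected one has 26, df 2, and is still of full rank. The standard error of b rises by roughly 1/√(1 − ρ²), which is 4%, 9% or 25% for ρ = .26, .4 or .6. That precision is gained at present only by imposing g = 0.

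The random-intercept repeat needs one more sentence. It adds two intercept variances and a covariance, so as listed it has 27 parameters on 28 moments and is identified only through the omitted group paths. With all group paths and both T0→T2 paths it has 29 parameters and rank 28, so it is not identified. Dropping the two T0→T2 paths from that repeat returns it to 27 parameters and df 1; constraining the lags is the alternative. The SAP should say which. In total this is two or three sentences and a few lines of syntax, with no new data.

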Moreover, we will focus on cognitive control and affective biases therein, because this process is related to RNT. We will measure two major constituents of cognitive control, i.e. working memory processing and motivational biases of cognitive control (with respectively a working-memory update/ignore emotion task and Pavlovian-to-instrumental transfer task) before and after MBCT/waitlist. We will use this behavioural data to assess whether working memory and motivational biases are indeed (i) related to RNT and MDD, (ii) are changed by MBCT and (iii) whether these changes are related to clinical effects of MBCT.

Additionally, we aim to investigate the timing of change by administering weekly self-report questionnaires.

Section 3: Study Methods

Design

Patients will be assigned to intervention (MBCT + TAU) or waitlist (TAU) based on regular clinical assessment procedure and start of treatment groups. The intervention group performs measurements once before (T0), halfway (T1), and once after MBCT (T2), whereas the waitlist performs measurements once before (T0), once during (T1), and once after a waiting period (T2) of at least 7 weeks, but preferably 8-10 weeks. The wait-list group receives MBCT after this waiting period and subsequently performs measurements halfway (T3) and after MBCT (T4).

Sample size – power calculation

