Before start of the study, a sample size calculation for the primary analysis (mediation analysis) was conducted using the Monte Carlo Power Analysis Application provided by Schoemann, Boulton, & Short (2017) (https://schoemann.shinyapps.io/mc_power_med/). This tool enables the researcher to calculate a required sample size for (simple) mediation models by using correlations between the independent variable (IV), dependent variable (DV), and mediator (M). We based the required sample size for the mediation analysis on previously published data on the effectiveness of MBCT for chronic, treatment-resistant depressed patients (Cladder-Micus et al., 2018). We based the calculation on 1000 replications, 20000 Monte Carlo Draws per replication, and a Confidence Level of 95%. The correlation between IV (condition; MBCT + TAU versus TAU) and DV (residual change in depressive symptom; $r = .18$), IV and mediator (residual change in RRS brooding score; $r = .27$), and mediator and DV ($r = .26$) were entered in the application. Based on this calculation, 174 participants would be required. Based on previous studies reporting a drop-out between 10% (Van Aalderen et al., 2012) and 24.5% (Cladder-Micus et al., 2018), we therefore expected a drop-out of 15% and aimed to include 200 participants.

Statistical analysis

Clinical effects of MBCT: replication and assessment of moderation

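### The PROCESS sensitivity analysis on residualised change scores understates the indirect effect and, if the arms differ mainly on one baseline measure, can produce a false one

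*SAP*

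**What the plan says.** Under Mediation analyses, the primary mediation test is a cross-lagged structural equation model (CLSEM). Its paths include "longitudinal cross-lagged effects of mediator and outcome variables, effect of outcome at T0 on outcome at T2 and mediator at T0 on mediator at T2", so both T0 scores enter that model.

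The section closes with a second analysis: "As a sensitivity analysis we will perform a simple mediation analysis by using the PROCESS macro". Group is the IV, the outcome is "pre- to post-treatment residualized change in depressive symptoms (IDS-SR) as DV", and "pre- to mid-treatment residualized change in RNT/rumination (PTQ/RRS brooding subscale) will be entered as mediator". No covariates are named and no formula for the residuals is given. The form is then extended: "Other potential mediators of interest will be tested in an analogues manner".

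Under Design, allocation is not random: "Patients will be assigned to intervention (MBCT + TAU) or waitlist (TAU) based on regular clinical assessment procedure and start of treatment groups". Under Clinical effects of MBCT, the arms are to be compared at baseline "on sociodemographic, outcome, and hypothesized mediating and moderating variables, independent-samples t-test or chi-square test will be used", but the result of those tests is not tied to the PROCESS model.

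**The concern.** In its usual meaning, a residualised change score is the residual of the later score after regression on its own T0 score in the pooled sample, with group left out. That has three consequences.

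- **Own baseline, without group.** If the arms differ on the T0 score, the first regression absorbs part of the group effect.
- **Other variable's baseline missing, group-to-mediator path.** RNT change is not adjusted for T0 IDS-SR. If T0 severity affects T1 RNT and the arms differ in T0 severity, that difference appears as an effect of group on the mediator.
- **Different adjustment on the two sides, mediator-to-outcome path.** The mediator is cleared of T0 RNT only and the outcome of T0 IDS-SR only. The slope between the two residuals is then not the adjusted slope, even with balanced arms.

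At stake is how to read the check. If it disagrees with the CLSEM, nobody can tell whether the cause is the data or the scoring. Agreement is no more informative.

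**Working it through.** **The plan's own figure.** The SAP gives no figure for the PROCESS check itself. The nearest is the sample size, which also rests on residual-change variables. From r = .18, .27 and .26, the paths are a = .27 and b = (.26 - .27 x .18)/(1 - .27^2) = .2114/.9271 = .228. At N = 174, joint significance gives power .81 and simulation gives .79 to .83. So 174 fits an 80% target, which the SAP does not state. This figure is not in dispute, and no baseline difference enters it.

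**Settings (assumptions; the SAP gives none of them).** Standardised scores, 87 per arm, T0 correlation .5, stability .6, path c from T0 IDS-SR to T1 RNT of .15 (or .25), T1 RNT to T2 IDS-SR .3, residual SD .75. The group effect t on T1 RNT is -.4 or 0, with group coded 1 for MBCT and 0 for TAU. True indirect effect: -.4 x .3 = -.12, or 0. dM and dY are the T0 differences (MBCT minus TAU) in RNT and IDS-SR.

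**Group-to-mediator path.** Residualising without group gives

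a = [t + c(dY - .5 dM)] x (1 - R2), with R2 = (dM^2/4)/(1 + dM^2/4).

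R2 is 2%, 6% and 14% at dM = .3, .5 and .8.

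- Both baselines .3 worse: (-.4 + .15 x .15) x .978 = -.369
- Both .5 worse: (-.4 + .15 x .25) x .941 = -.341
- Both .8 worse: (-.4 + .15 x .40) x .862 = -.293
- Both .5 better: (-.4 - .15 x .25) x .941 = -.412

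**Mediator-to-outcome path, balanced arms.** The residualised mediator is .15u + e, where u is T0 IDS-SR less .5 times T0 RNT. Its variance is .15^2 x .75 + .5625 = .5794. The mediator part of the residualised outcome is .3(.6w + e), where w is T0 RNT less .5 times T0 IDS-SR, and cov(u, w) = -.375. So b = .3 x (.5625 - .15 x .6 x .375)/.5794 = .1586/.5794 = .274, against a true .300. The indirect effect is -.4 x .274 = -.110, 9% too small. With c = 0 the formula returns b = .300.

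**Simulated indirect effect (2000 replicates, true value -.12).**

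| T0 difference, both measures | Residualised | Loss |
|---|---|---|
| none | -.107 to -.110 | 8-11% |
| MBCT .3 SD worse | -.103 | 14% |
| MBCT .5 SD worse | -.095 | about 20% |
| MBCT .8 SD worse | -.084 | 30% |
| MBCT .3 SD better | -.111 | 7-8% |
| MBCT .5 SD better | -.106 | 12% |

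In the three rows with MBCT worse, power is about 84%, 80% and 68%. With both T0 scores as covariates the estimate is -.119 to -.120, with power about 90%, 88% and 85%.

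**No group effect on the mediator (true indirect effect 0).**

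- IDS-SR only, .5 SD: a = .15 x .5 = .075 or .25 x .5 = .125. It is significant in 8-9% and 15-17% of trials.
- IDS-SR only, .3 SD, c = .15: 6%.
- Both measures, .5 SD: a = .15 x .25 x .941 = .035 or .25 x .25 x .941 = .059. It is significant in about 6% for either.
- With both T0 scores as covariates: 4-5%.

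**Second set of settings.** Stability was .5, residual SD .7, with an added T0 RNT to T2 IDS-SR path of .1. With c = .2 and balanced arms, b is .247 against .300. With MBCT .5 SD worse on both measures, the indirect effect is -.060 against a true -.090, with power 52% against 75% using both covariates. With IDS-SR alone .5 SD apart, false positives are 12% (c = .2) and 20% (c = .3). With equal .5 SD imbalance on both they are 4-6%. With neither cross-lagged path there is no false effect, and a true -.090 is estimated at -.090, -.087 and -.081 for imbalances of .3, .5 and .8 SD.

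**The case against.** Much of the case on the other side stands.

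- **Scope.** This is a sensitivity analysis. A reader might infer that the primary mediation result is compromised. It is not, because the CLSEM carries both T0 scores through its autoregressive and cross-lagged paths.
- **Reading of the text.** The SAP does not say that the residuals are formed without group or on the own baseline only. That is the usual meaning of the term together with a simple mediation model, not something the document states.
- **Cause.** It is tempting to blame the whole bias on non-random allocation. About a tenth of the effect is lost with balanced arms under the first settings, so most of the 14% at .3 SD has nothing to do with allocation.
- **Direction.** The largest losses put the MBCT arm worse on both measures. With MBCT better by .3 or .5 SD the loss is about 7-12%, close to the balanced case. The SAP gives neither size nor sign of any imbalance.
- **False effects.** A reader might infer that clinically assigned arms generally yield a false indirect effect here. They do not: equal imbalance on both measures leaves the rate near 5%, and without the T0 IDS-SR to T1 RNT path there is no false effect.

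One further argument is that the PROCESS form matches the one behind the power calculation. That is true, but the SAP's reference list describes the source of those correlations as a randomised trial, and continuity is a weak reason to keep an estimator that the covariate form matches or beats on bias in the scenarios run.

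**Conclusion.** The point holds as a recommendation on the sensitivity analysis. Read in the usual way, the planned form understates the indirect effect: by about 10% with balanced arms, by about 14%, 20% and 30% with the MBCT arm .3, .5 and .8 SD worse on both baselines, and by about 12% with it .5 SD better. A false effect needs an imbalance mainly on one measure plus an effect of T0 IDS-SR on T1 RNT. For a .5 SD difference in T0 IDS-SR and paths of .15-.25, false positives run at about 9-17%.

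The sizes are illustrative, since they rest on assumed imbalances, paths and correlations. The balanced-arm loss also depends on that cross-lagged path. The plan itself treats the path as possible by including cross-lagged effects in the CLSEM. The primary analysis and the sample size are not called into question here.

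**What to change.** In the PROCESS analysis, replace the residualised change scores. Enter group as IV, T1 RNT (PTQ or RRS brooding) as mediator and T2 IDS-SR as outcome, with T0 RNT and T0 IDS-SR as covariates in both equations. Use the same form for the other mediators.

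Both T0 scores are needed in both equations. Adjusting each equation for its own T0 score alone is not enough: under the second settings, with IDS-SR alone .5 SD apart and a path of .3, it gives 27% false positives, against 20% for the residualised form and 5% with both.

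If residualised scores are kept for continuity with the power calculation, the SAP should state how the residuals are formed and report them beside the covariate version.

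The cost is SAP wording only. The macro and the four scores are the same, and no further participants are lost, because the residuals already require all four scores. The change does not deal with unmeasured confounding from clinical assignment, and the report should say so.
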